8.1.2 Participant Satisfaction

Participant satisfaction data will be collected via written questionnaires at the final 12-week follow-up visit. These questionnaires have been developed based on questions used in previous CoolSculpting studies and modified to pertain to specific body areas treated (upper arms and inner thighs). One or two questionnaires will be provided depending on the body areas treated (upper arms and/or inner thighs). For the upper arm participant satisfaction questionnaire, see Section [15.3.1](#). For the inner thigh participant satisfaction questionnaire, see Section [15.3.2](#).

8.1.3 Caliper Measurement

Caliper measurements of the treatment areas will be taken at pre-treatment and at 12-weeks post final treatment. After the treatment area is identified and marked, the thickness of the fat layer will be measured using a caliper at the middle of the fat bulge. For each treatment area, 3 measurements will be taken and recorded. The average of the three measurements will be calculated. The location of where measurements are taken will be recorded on a transparency sheet or equivalent, along with reference points using the participant's body landmarks (such as a mole, skin pigmentation, etc). This transparency may be used at the post treatment visit to locate the measurement sites. In addition, to further ensure the quality and consistency of the

measurements, the same staff member should perform the caliper measurements for each participant. For further details on caliper measurements, please see Section [15.4](#).

8.2 Safety Assessments

Throughout the course of the study, all AEs will be monitored and reported on an AE CRF, including seriousness, severity, action taken, and relationship to study treatment. If AEs occur, the first concern will be the safety of the study participants.

Safety will be monitored by documentation of AEs and clinical assessment of the treatment sites. Post-treatment sensory changes outside of treatment areas will also be documented and assessed.

8.2.1 Adverse Events

Throughout the course of the study, all AEs will be reported and monitored on an AE CRF, including event name, duration, seriousness, relatedness, severity, action taken, and outcome. If AEs occur, the first concern will be the safety of the study participants. AEs and device deficiencies are to be recorded on the corresponding CRF for the participant upon the site becoming aware of said event. Additionally, SAEs and UADEs will be reported using SAE forms within 24 hr of awareness.

AEs will be collected throughout the study once there is a signed ICF. At each visit, the investigator or designated study staff will solicit and assess the participant for AEs. Previously recorded AEs and changes in therapy/concomitant medications are to be updated as necessary. All reportable AEs and clinically significant abnormal laboratory findings will be documented on the appropriate CRF.

Adverse Event Definition

An AE is defined in accordance with ISO 14155 as any untoward medical occurrence, unintended disease or injury, or untoward clinical signs (including abnormal laboratory findings) in participants, users, or other persons, if related to the investigational medical device. This definition includes events related to the investigational medical device or comparator and events related to the procedures involved. Disease signs and symptoms that existed before the study treatment are not considered AEs unless the condition recurs after the participant has recovered from the pre-existing condition or the condition worsens in intensity or frequency during the study.

AEs will be monitored throughout the study once the participant has signed the ICF. At each post-baseline visit, the investigator will begin querying for AEs by asking each participant a general, non-directed question such as “Have you had any changes to your condition since your last visit?” Previous AEs and changes in therapy/concomitant medications are to be updated. Directed questioning and examination will then be done as appropriate. All reportable AEs and clinically significant abnormal laboratory findings will be documented on the appropriate eCRF.

Adverse Device Event

An ADE is defined in accordance with ISO 14155 as “an adverse event related to the use of an investigational medical device.” This definition includes any AEs resulting from insufficient or inadequate instructions for use, deployment, implantation, installation, or operation, or any malfunction of the investigational medical device as well as any event resulting from use error (per ISO 62366) or from intentional misuse of the investigational medical device.

Device Deficiency or Complaints

A device deficiency is defined in accordance with ISO 14155 as inadequacy of a medical device including issues with respect to its identity, quality, durability, reliability, safety, or performance. Device deficiencies include malfunctions, use errors, and inadequate labelling.

If a device deficiency occurs, the investigator will notify Allergan using the CRF. Device deficiencies shall be documented throughout the study and appropriately managed by Allergan. The Clinical Trial Site will enter all the information regarding device deficiency into the appropriate CRFs. Device deficiencies associated with AEs will also require completion of SAE forms. Allergan shall review all device deficiencies and determine and document in writing whether they could have led to a SADE. These shall be reported to the regulatory authorities and IRBs as required by Federal regulations.

Assessment of Severity

Severity is a clinical determination of the intensity of an AE. The severity assessment for a clinical AE will be assigned a category by the investigator as follows:

Mild	An AE that is easily tolerated by the participant, causes minimal discomfort, may require only minimal treatment and does not interfere with everyday activities.
Moderate	An AE that is sufficiently discomforting to interfere with normal everyday activities; intervention may be needed, but poses no significant or permanent risk of harm.
Severe	An AE that prevents normal everyday activities; treatment or other intervention usually needed.

If there is a change in severity of an AE, it must be recorded as a separate event.

Assessment of Causality

Relationship to a device refers to a determination of the relationship (if any) between an AE and the device. A causal relationship is present if the investigator determines that there is a reasonable possibility that the AE may have been caused by the device.

An AE could be considered procedure-related when, in the judgment of the investigator, it is reasonable to believe that the event is associated with the procedure, regardless of the relationship to the study device. Procedure-related causes that contribute to the occurrence of the

event can be attributed to other products, surgical techniques, or medications required specifically for the procedure.

Every effort will be made by the investigator to assess the relationship of the AE, if any, to the device and/or study procedure. Causality should be assessed using the categories presented in the following table:

Not related	Clinical event of which the relationship to the device and/or procedure can be excluded, such as if the event has an incompatible time relationship to study procedure and/or use of the device, involves a body part or organ not expected to be affected by the device or procedure, could be explained by underlying disease or other drugs or chemicals or is incontrovertibly not related to the study device, and is not due to use error.
Unlikely	Clinical event whose time relationship to use of the device and/or study procedure makes a causal connection improbable, but that could plausibly be explained by underlying disease or other drugs or chemicals.
Possible	Clinical event with a reasonable time relationship to the use of the device and/or study procedure, but that could also be explained by concurrent disease or other drugs or chemicals. Cases where relatedness cannot be assessed or no information has been obtained should also be classified as possible.
Probable	Clinical event with a reasonable time relationship to the use of the device and/or study procedure, and is unlikely to be attributed to concurrent disease or other drugs or chemicals.
Causal relationship	Clinical event with plausible time relationship to the use of the device and/or study procedure, is a known side effect of the product category the device belongs to or of similar devices and procedures; follows a known response pattern to the medical device; involves a body-site or organ that the device or procedures are applied to and/or influence; harm is due to error in use, and that cannot be explained by concurrent disease or other drugs or chemicals.

Follow-up of Adverse Events

All investigators should follow up with participants with AEs until the event is resolved or until, in the opinion of the investigator, the event is stabilized or determined to be chronic. Details of AE resolution must be documented in the CRF.

Documentation and Reporting of Adverse Events

AEs should be reported and documented in accordance with the procedures outlined below. All AEs occurring during the study must be documented on the relevant CRF pages. The following data should be documented for each AE in the appropriate CRF fields:

- Description of the symptom event.
- Classification of ‘serious’ or ‘not serious.’
- Severity.
- Date of first occurrence and date of resolution (if applicable).
- Action taken.
- Causal relationship.
- Outcome of event.

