Third Degree Burn	Third degree burns are deeper still, involving all layers of the skin. Because the nerves and blood vessels are damaged, third degree burns appear white, leathery, and tend to be relatively painless.
Cold-induced Panniculitis	Severe inflammation which requires medical or surgical intervention.
Skin Pigment Changes	The appearance of hyperpigmentation or hypopigmentation in the treatment area.
Infection	Infection at the treatment site, diagnosed by a physician and requiring medical intervention.
Discomfort During Procedure	Discomfort reported during the procedure that is intolerable to the participant and results in an interruption or discontinuation of the procedure
Discomfort Post Procedure	Significant discomfort, pain, cramping, tenderness, soreness, muscle spasm following the procedure which results in medical intervention (physician visit and/or prescription pain reliever)
Prolonged Sensory Alteration Post Procedure	Sensory changes (numbness, tingling, burning sensation) that are prolonged (ie, lasting longer than 12 weeks).
Sensory Alteration Requiring Medical Intervention	Sensory changes (pain, burning, stinging, hypersensitivity) with a severity warranting medical intervention.
Vasovagal Symptoms	The occurrence of symptoms of anxiety, light-headedness, dizziness, nausea, sweating, near syncope, or syncope (fainting).
Contour Irregularity	Significant indentation or contour irregularity in the treatment area that would require surgical intervention.
Allergic/Irritant Contact Dermatitis	Itchy rashes and skin peeling that may result from prolonged exposure to gel pad or applicator pressure
Subcutaneous Induration	Hardness within the treatment area, either as general firmness or discrete nodules.
Paradoxical Hyperplasia	Visibly enlarged tissue volume within the treatment area which may develop 2-5 months after treatment.
Hernia	Creation or exacerbation of hernia. Hernia is defined as a protrusion of an organ or the fascia of an organ through the wall of the cavity that normally contains it.
Treatment Area Demarcation	Treatment area demarcation: excessive fat removal in the treatment area causing unwanted indentation
Other	Any other untoward medical event determined by the investigator to be an adverse event, regardless of the relationship to the device or treatment.

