8.2.1.1 Serious Adverse Events

Serious Adverse Event Definition

An SAE is defined as an AE that:

- led to death
- led to serious deterioration in the health of the participant, that either resulted in
 - a life-threatening illness or injury; or
 - a permanent impairment of a body structure or a body function, or
 - in-patient or prolonged hospitalization; or
 - medical or surgical intervention to prevent life-threatening illness or injury or permanent impairment to a body structure or a body function; or
 - if a participant becomes pregnant, then spontaneous abortion, fetal distress, fetal death, or a congenital abnormality or birth defect is considered an SAE

In addition, medical and scientific judgment is required to decide if prompt notification is required in situations other than those defined for SAEs above. This may include any event that the investigator regards as serious that did not strictly meet the criteria above but may have jeopardized the participant or required intervention to prevent one of the outcomes listed above, or that would suggest any significant hazard, contraindication, side effect, or precaution that may be associated with the use of the investigational product.

Serious Adverse Device Effect (SADE)

All device or surgical related SAEs must be entered into the EDC system within 24 hours of being notified of the event. The sponsor will be notified by EDC system once the SAE electronic form has been submitted.

- The relationship of the clinical event to the devices and procedure should be reported on the Form and will be determined by the investigator.
- Following evaluation of each SAE, the responsible ethics committee will be notified as appropriate based on national regulations.
- All SAEs that occur from the time the ICF is signed through to their final study visit must be reported to the sponsor. In addition to entering the information into the EDC system, the investigator must:
- Notify the sponsor immediately (within 24 hours) by emailing the Allegan Product Surveillance team at: [contact]

The following SAE information should be provided:

- Description of the symptom event (including treatment dates, areas treated, event description, etc)
- Applicator(s) and Serial Number used during treatment
- Classification of ‘serious’ or ‘not serious’
- Severity
- Date of first occurrence and date of resolution (if applicable)
- Action taken
- Causal relationship

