9.2. Adverse Events

An AE is any untoward medical occurrence, unintended disease or injury, or untoward clinical signs (including abnormal laboratory findings) in participants, users or other persons, whether or not related to the investigational medical device or the comparator device. This definition includes events related to the procedures involved.

An SAE is defined as an AE that:

- led to death
- led to serious deterioration in the health of the participant, that either resulted in
 - a life-threatening illness or injury; or
 - a permanent impairment of a body structure or a body function, or
 - in-patient or prolonged hospitalization; or
 - medical or surgical intervention to prevent life-threatening illness or injury or permanent impairment to a body structure or a body function; or
 - if a participant becomes pregnant, then spontaneous abortion, fetal distress, fetal death, or a congenital abnormality or birth defect is considered an SAE

AEs will be coded using MedDRA V22.1 or higher.

AEs will be defined as treatment-emergent if they start after the first treatment. AEs with missing or partial dates will be handled according to Section **Error! Reference source not found.** with respect to assigning treatment-emergence. As a conservative approach, AEs are considered treatment-emergent unless there is clear indication that the event occurred before the first treatment in the study. In general, only TEAEs will be included in the summary tables, but all AEs will be included in the listings.

The number of participants and the number of TEAEs will be tabulated by SOC and PT, sorted by the decreasing overall frequency of SOC and then by PT in decreasing frequency within each SOC. For summaries by SOC, PT, and maximum severity, a participant will be counted once at the highest severity level for which the event occurred at the SOC level and the highest severity level for each unique PT within that SOC level. Therefore, participants will only contribute once to each PT and once to each SOC level. Severity will be assessed as mild, moderate, or severe. For summaries by SOC, PT, and maximum

This document is confidential.

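### Protocol 8.2.1 defines an adverse event only if it is related to the device (or procedure), while SAP 9.2 and the protocol's own recording text cover unrelated events too

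*Protocol*

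**What the plan says.** The formal definition in Protocol 8.2.1 covers untoward occurrences "in participants, users, or other persons, if related to the investigational medical device". The sentence after it reads "This definition includes events related to the investigational medical device or comparator and events related to the procedures involved". Taken together, the two sentences admit events related to the device or to the procedure, and no others.

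SAP 9.2 opens its definition in nearly identical terms but ends it differently: "in participants, users or other persons, whether or not related to the investigational medical device or the comparator device".

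Other parts of the protocol treat unrelated events as AEs:

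- The last row of the potential adverse effects table in section 4.2.1.2 takes in "Any other untoward medical event determined by the investigator to be an adverse event, regardless of the relationship to the device or treatment".
- The lowest level of the causality scale in section 8.2.1 is a "Clinical event of which the relationship to the device and/or procedure can be excluded".
- Section 8.2.1.1 asks the investigator for a written case history of each serious adverse event (SAE), saying whether it was related to the device or procedure or was not.

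The general recording rules are broad: "All AEs occurring during the study must be documented on the relevant CRF pages" in section 8.2.1 and "All SAEs that occur from the time the ICF is signed through to their final study visit must be reported to the sponsor" in section 8.2.1.1. An SAE is itself built on the AE definition: "An SAE is defined as an AE that" meets one of the listed outcomes.

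The visible items in SAP section 12 concern day numbering, the safety population, and arms or thighs in place of participants. None mentions the AE definition.

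**The concern.** Sites record events under the protocol, and the tables are built under the SAP. If the two documents define the event differently, the tables can claim to count something that was never collected.

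The direction is known. An omitted unrelated event lowers the TEAE event count, and it lowers the proportion of participants with a TEAE or leaves it unchanged. It cannot raise either. The loss is also permanent: SAP 6.1 plans a listing of all AEs, but an event that never reached the case report form is in no listing.

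AEs and SAEs are the stated safety endpoint, and Protocol 4.2 says the data are to help support a regulatory submission. SAP section 10 also shows TEAEs by investigational site, so if sites read the definition differently, part of any difference between sites would be an artefact of recording.

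**Working it through.** No arithmetic applies, and the plan gives no figure to reproduce. The check sets the passages side by side.

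**1. Which events fall under each definition?**

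| Event | Protocol 8.2.1 definition, read literally | SAP 9.2 definition |
|---|---|---|
| Related to the device | AE | AE |
| Related to the procedure, not the device | AE (by the second sentence) | AE |
| Related to neither | Not an AE | AE |

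The conflict is confined to the last row, but there it is complete.

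**2. Does the rest of the protocol support the restriction?** No.

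- A causality level for events whose relationship is excluded would have no use if such events were not AEs.
- The open row in the table of section 4.2.1.2 disregards relationship in express terms.
- Section 8.2.1 collects AEs from signed consent, which is before any device exposure.
- Section 9.3.3 plans separate summaries of AEs and of adverse device events. Under the literal definition these would differ only by events related to the procedure but not to the device.

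**3. Do the general recording rules override the definition?** Not by themselves. The instructions to document all AEs and to report all SAEs depend on what an AE is. Because an SAE is defined as a kind of AE, the condition formally passes into the SAE definition as well.

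**4. Could the condition apply only to users and other persons, leaving participants unrestricted?** That reading would fit the rest of the protocol, but not the sentence. The comma before the condition sets it off from the whole list of persons, and the next sentence speaks only of related events without separating participants from others.

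**5. What reaches the tables?** SAP 9 and 9.2 summarize TEAEs and serious TEAEs, including tables by system organ class and preferred term. All of these draw on recorded events. Events unrelated to both device and procedure are the ones at risk, and no later analysis step can restore them.

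**6. How large is the effect?** It would need the rate of unrelated events over about 3 months and the share of sites reading the definition literally. The documents give neither.

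**The case against.** The strongest reply is that this is a slip in one clause which the operating text corrects. Sites are to ask a non-directed question about any change in condition from signed consent onward. They complete a causality field for every event, they have an unrelated level to choose, and the protocol speaks of a relationship only if there is one. Someone working through that form is told repeatedly that unrelated events belong on it. Source-document verification under Protocol 10.2 is a further check. The analyses are descriptive (SAP section 2), and no effectiveness result is touched.

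Much of this stands, and it limits the practical risk. It does not make the definition right. A monitor who checks against the protocol definition would not see a missing unrelated event as an omission. The visit procedures in Protocol section 7 are blacked out and may hold clearer instructions, but they could not cure a visible definition that says the opposite.

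Three stronger readings are tempting, and the documents do not support them.

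- *Unrelated SAEs will be lost.* The definition formally allows it, but section 8.2.1.1 requires all SAEs from consent to final visit and asks whether each was related. That presupposes unrelated SAEs, so their loss is unlikely.
- *The loss can be expressed in percentage points.* Dividing one participant by the planned 42, or by an assumed number per site, gives only the step for one participant. It would be the same for any safety question in this trial and says nothing about how many events would go unrecorded.
- *The SAP's adverse device event rules are a second contradiction.* SAP 9.3 states no causality level, while SAP 9.2 counts unlikely and above as related. The natural reading carries the 9.2 rule over. Causality is recorded for each event, so any other cut can be derived later.

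**Conclusion.** The conflict is real, and the Protocol 8.2.1 definition is wrong as written. Events related to neither device nor procedure fall outside it, but inside the SAP 9.2 definition and inside what the protocol's own recording text assumes.

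The consequence is a risk and not a certainty. It materializes only if a site follows the formal definition over the surrounding instructions. If that happens, TEAE counts can only be too low, and neither listings nor re-analysis can correct them. The size cannot be stated from the documents.

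This rests on reading the definition as punctuated and on the visible text alone. It would be wrong to infer that safety data are bound to be incomplete, because most of the protocol points sites to full recording.

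**What to change.** In Protocol 8.2.1, replace the closing condition of the definition, from the word *if* onward, with the whether-or-not condition of SAP 9.2, as it applies to the investigational device. The sentence on device- and procedure-related events can stay, since it would then illustrate the definition without limiting it. Confirm to sites in a short memo that all events are to be recorded whatever their relationship.

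If the protocol is not amended, record the difference between the two definitions in SAP section 12. That discloses the problem but does not recover events already left out.

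The cost is a one-phrase amendment with the ethics committee or review board approval that Protocol 12.1 requires, a brief memo, and a few more events for sites to record. No treatment rule or effectiveness analysis changes.
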